14.6 Parasite clearance time

Parasite clearance time is the duration (in days) between first dosing and the first blood draw with parasite clearance (parasite count = 0). The subsequent readings up till at least 6 hours from the first zero reading must remain zero for the presence of parasites.

[figure not shown]
The same ICEs and strategies as defined for time to fever clearance (see Section 14.5) will be applied to parasite clearance time, with the exception of intake of concomitant medications with impact on fever, which is not an ICE for parasite clearance time. Since parasite clearance time is measured in days, censoring will be done at the day of the last available microscopy assessment.

The same analysis approaches as described for fever clearance time are applicable also to parasite clearance time (note that for the target population for parasite clearance time the prerequisite of showing an increased temperature does not hold). Participants with no parasite clearance or ICEs will be censored at the day of the last microscopy assessment.

CCI

CCI

15 Safety Analyses

This section includes specifications for summarizing safety endpoints that are common across clinical studies such as adverse events, laboratory tests, and vital signs.

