### Parasitological Assessments

Parasite density expressed as the number of asexual parasites per  $\mu\text{L}$  will be measured serially to determine PCT. Blood sampling for genotyping will be done by extracting specific blood samples for this purpose.

Blood smears preparation, staining, examination, and interpretation should be in accordance with the current WHO 2003 protocol (WHO 2003: Assessment and monitoring of antimalarial drug efficacy for the treatment of acute uncomplicated *P. falciparum* malaria; Chapter 8: Technical Considerations and Quality Assurance). Should a clinical study site have established procedures deviating from the WHO 2003 protocol, the nature and the reason of the deviations must be discussed and approved by the Sponsor before the study commences.

Thick and thin blood films for parasite count should be obtained and examined at Screening to confirm inclusion/exclusion criteria. Thick blood films will be examined every 6 hours ( $\pm 0.5$  hours) for the first 72 hours (Days 1 to 4): 2 negative readings taken 6 hours apart. Thick blood films will be also examined on Days 8, 15, 22, 29, and 43 or at any unscheduled visit (specific details provided in [Table 1](#) and [Table 2](#)).

Additionally, blood films should be obtained whenever parasitological reassessment and genotyping is required. A thin blood smear will also be taken in case of reappearing parasitemia, to confirm *Plasmodium* species. The method of counting parasites will be described in a Laboratory Manual including gametocyte counts. Local quality control of slides is to be assured by reading of slides by 2 different qualified microscopists, reporting independently, with the arithmetic mean of the 2 counts being recorded in the patient record and CRF. In the case of discrepancy, a third microscopist will review the slides and the Site Principal Investigator will make the final classification to be reported in the CRF. An external quality control of slide reading may be established by an independent laboratory.

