9.9 Definition of Duration, 'Time to' and 'Time Since' Variables

Duration will be calculated as the difference between start and end dates plus 1 (e.g., the duration of an Adverse Event (AE) = AE end date – AE start date + 1). Durations will be calculated only when both dates are available, i.e. imputed dates will not be used to compute the duration unless otherwise specified.

The time to an event will be calculated as date of event – reference date + 1 (e.g., ADT – STARTDT + 1). If time to an event is calculated in hours, then it is calculated as the difference between event and reference SAS datetimes divided by 3600 (e.g., (ADTM – STARTDTM) / 3600).

The time since an event will be calculated as:

- Date of event – reference date + 1, if the date of event is equal or greater than the reference data (e.g., days in study at onset of AE = AE start date – date of randomization + 1)
- Reference date – date of event otherwise (e.g., days since diagnosis = date of randomization – date of diagnosis)

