14.5 Fever clearance time

Fever clearance time is defined as the time (in hours) from first dosing to the first measurement of temperature $< 37.5^{\circ}\text{C}$ for 2 consecutive temperature readings, plus confirmed normal temperature ($< 37.5^{\circ}\text{C}$) 24 hours after the first normal body temperature reading. Participants who are initially included on documented history of fever and who do not subsequently have a documented temperature reading of $> 37.5^{\circ}\text{C}$ at the pre-dose visit or during the 24 hours following initial dosing will not be considered for the population-level summary.

For fever clearance time, the ICEs as defined by the study protocol will be identified and handled as described in the following:

- **Intake of rescue medication:** See Section 14.1 for description of rescue medication. A composite variable strategy is applied, i.e., time to fever clearance is censored at the time of rescue medication intake. In order to qualify as ICE, the intake of rescue medication has to take place within the first 3 days after treatment initiation.
- **Intake of concomitant medications as a continuous treatment that have an impact on fever:** Filtering concomitant medications programmatically for paracetamol, acetaminophen, NSAIDs (ibuprofen, naproxen), salicylic acid, and by medical review. A composite variable strategy is applied, i.e., time to fever clearance is censored at the time of first concomitant medication intake. In order to qualify as ICE, the start date of intake of concomitant medication has to take place within the first 3 days after treatment initiation. If the fever medication was taken prior to dosing, participants will still be included for analysis. Strategies for intercurrent events will not apply.
- **Intake of prohibited medication that impacts treatment effect (e.g., drug with antimalarial activity):** Filtering concomitant medications programmatically for sulphadoxine-trimethoprim, doxycycline, quinolone antibiotics including fluoroquinolones, azithromycin, erythromycin and all other macrolides and by medical review. A composite variable strategy is applied, i.e., time to fever clearance is censored at the time of prohibited medication intake. In order to qualify as ICE, the intake of prohibited medication has to take place within the first 3 days after treatment initiation.

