- **Experience of any event that affects absorption (i.e., vomiting within the study intervention absorptive period of $2 \times \text{median } t_{\text{max}}$) or immune response (severe immunocompromised participants):** See Section 14.1 for description of events affecting absorption or immune response. A treatment policy strategy is applied, i.e., treatment effect is estimated regardless of intercurrent event.
- **Premature study discontinuation due to lack of efficacy:** See Section 14.1 for description of ICE. An on-treatment strategy is applied, i.e., time to fever clearance is censored at the day of the last available body temperature assessment. Note: If premature study discontinuation occurs after fever clearance has already been observed, then the strategy will not be applied.
- **Death due to malaria:** See Section 14.1 for description of death due to malaria. An on-treatment strategy is applied, i.e., time to fever clearance is censored at the day of the last available body temperature assessment. Note: If death occurs after fever clearance has already been observed, then the strategy will not be applied.

Median fever clearance time and 95% CIs will be estimated by use of the Kaplan-Meier method. Confidence intervals will be calculated using log-log transformation. Participants with no fever clearance or ICEs will be censored at the day of the last temperature assessment. Kaplan-Meier plots including a table with number of participants at risk and number of events will be provided. To explore whether there is an impact of dose group (Part A vs. Part B Cohort B0), age (continuous), sex, and parasite density at baseline on time to fever clearance, a Cox Proportional Hazards model will be applied.

[figure not shown]

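### Parasite clearance time is set in days, so SAP 9.9's date-difference-plus-1 rule reduces 12 six-hourly film times to 3 or 4 values, all longer than the elapsed time

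*SAP*

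**What the plan says.** SAP 14.6 gives the unit twice. The definition reads "Parasite clearance time is the duration (in days) between first dosing and the first blood draw with parasite clearance (parasite count = 0"), and the censoring sentence repeats it: "Since parasite clearance time is measured in days, censoring will be done at the day of the last available microscopy assessment".

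SAP 9.9 has two rules that could apply to a quantity in days, and both work on calendar dates. For durations: "Duration will be calculated as the difference between start and end dates plus 1". For times to event: "The time to an event will be calculated as date of event – reference date + 1". Clock time enters only under a third rule: "If time to an event is calculated in hours, then it is calculated as the difference between event and reference SAS datetimes divided by 3600".

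The sister endpoint is in hours. SAP 14.5 says "Fever clearance time is defined as the time (in hours) from first dosing". Section 14.6 takes over the Kaplan-Meier and Cox methods of 14.5, including the comparison introduced by "To explore whether there is an impact of dose group (Part A vs. Part B Cohort B0").

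Protocol 8.1 (Parasitological Assessments) schedules a thick film every 6 hours for 72 hours and says that parasite density "will be measured serially to determine PCT". It defines the endpoint as running to the time of the blood draw and names no unit.

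**The concern.** The schedule resolves clearance to 6 hours, but the analysis rule counts calendar dates. Three effects follow. Distinct film times merge into a few values. The plus 1 makes a quantity labelled as a duration longer than the time that passed. And two participants who clear after the same number of hours can receive different values because one was dosed in the morning and the other in the evening, which has nothing to do with drug effect.

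At stake are the reported median, the Kaplan-Meier curve and the exploratory Part A versus Cohort B0 Cox model. Cohorts B1 to B3 were not enrolled (SAP 7), so these two small cohorts supply all the parasite clearance evidence the study will give.

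**Working it through.** The plan states no clearance time or other figure on this point, so there is nothing to reproduce. The check applies the written rule to the written schedule.

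**Inputs**
- Unit: days (SAP 14.6).
- Rule for days: date difference plus 1 (SAP 9.9). The duration rule and the time-to-event rule give the same result.
- Films: 72/6 = 12 post-dose films at t = 6, 12, ..., 72 h (Protocol 8.1 and Table 2).
- Clock hour of first dose, u: not given in the documents, so all of 00:00 to 23:59 is covered.

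**Formulas**
- Coded days = floor((u + t)/24) + 1.
- Excess in hours = 24 × coded days − t.

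**Example, clearance at 30 h (1.25 days elapsed)**
- Dosed at 09:00: floor(39/24) + 1 = 2 days; excess 48 − 30 = 18 h.
- Dosed at 20:00: floor(50/24) + 1 = 3 days; excess 72 − 30 = 42 h.

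**All nominal film times**

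| Film time (h) | Coded days | Higher value applies if dosed from | Excess (h) |
|---|---|---|---|
| 6, 30, 54 | 1 or 2; 2 or 3; 3 or 4 | 18:00 | 18 or 42 |
| 12, 36, 60 | 1 or 2; 2 or 3; 3 or 4 | 12:00 | 12 or 36 |
| 18, 42, 66 | 1 or 2; 2 or 3; 3 or 4 | 06:00 | 6 or 30 |
| 24, 48, 72 | 2; 3; 4 | no change | 24 |

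- Dosed before 18:00, the 12 films give the values 1, 2, 3 and 4. Dosed at 18:00 or later, they give 2, 3 and 4.
- Nine of the 12 film times change value with the dosing hour.
- The excess runs from 6 to 42 h. If film times move within the ±30-minute window of SAP 9.4, it runs from just above 0 to just under 48 h.
- The direction is certain: floor(x) + 1 > x, and x = (u + t)/24 is at least t/24. Since every value is too long, an uncensored median is too long as well.
- Under the hours rule the same films give 12 distinct nominal values with no shift.

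The count of 3 or 4 concerns the 72 hours of six-hourly films. Clearance first seen at Day 8 or later would add values.

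**Effect on the median.** The coded median can only be a whole day, or a half day by the midpoint convention when n is even. How far it moves depends on inputs the documents do not give. As an illustration, assume 25 participants, lognormal clearance with log-SD 0.35, each time rounded up to the next six-hourly film, and films continued past 72 h as a simplification. With a true median of 30 h, the coded median is 2 days in 11% to 94% of simulated trials across six assumed dosing windows. With a true median of 18 h it is 2 days in 100% of trials in those windows, but in only 50% if all dosing falls between 00:00 and 06:00. With a true median of 24 h it is 2 days in 89% to 100%, but in only 50% if all dosing falls between 20:00 and 24:00.

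**Effect on the Cox model.** Coding in days adds ties. For 12 versus 25 participants with true medians 6 h apart and log-SD 0.25 to 0.5, an uncensored model without covariates kept 15% to 93% of the information available in hours. That range is too wide to support a single figure, and the SAP model also includes age, sex and baseline parasite density.

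**The case against.** **The plus 1 may be only a day number.** Protocol Section 3 and SAP 9.8 place the start of treatment on Day 1, so 7 days after treatment is Day 8, and the rule in 9.9 reproduces that numbering. Multiplying a day number by 24 is the reader's step, not the plan's. If a coded day d is read as d − 1 days after treatment, the mean offset of the median is −8 to +12 h in the same kind of simulation (n = 25, true medians 18 to 48 h). This is a fair point about labelling, but it does not dispose of the matter: 14.6 calls the value a duration, and coarseness and dependence on the dosing hour remain under either reading.

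**Section 14.6 might override 9.9.** A figure follows the definition and is not shown in the text available here, and a specific section may depart from a general one. A programmer could also divide elapsed hours by 24. Neither can be excluded, but no visible sentence says either. Nor does day-level censoring language by itself prove whole-day arithmetic, since 14.5 uses such language for an endpoint in hours. The argument rests on the stated unit together with 9.9.

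**Little depends on it.** This stands. The endpoint is descriptive, individual data are listed as measured (SAP 9.3), and the remaining cohort comparison is exploratory and not randomised.

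A reader might also infer a departure from the protocol. The documents do not support that: the protocol sets no unit, and its Section 9.4 leaves analysis details to the SAP.

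**Conclusion.** The point holds as an inconsistency within the SAP and an avoidable loss of resolution in a descriptive secondary endpoint. The 3 or 4 values, the 6 to 42 h excess at nominal times and the nine film times that depend on the dosing hour follow from the text alone, provided the unseen figure in 14.6 does not override 9.9.

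The size of the effect on the median and on the Cox model is not established. A reader might infer that cohorts with true medians of 18 h and 24 h would both be reported as 2 days, or that the dosing hour matters only over some middle range of medians. Both statements fail for other plausible dosing windows.

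A reader might also see a contradiction between SAP 7, which censors at medication intake, and Sections 5 and 14.6, which censor at the last microscopy. The text is ambiguous rather than contradictory. Section 14.6 imports the strategies of 14.5, including censoring at intake, and its microscopy sentence can be read as replacing only the last-temperature rule.

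**What to change.** In SAP 14.6, define parasite clearance time in hours as (film datetime − first-dose datetime)/3600, which is the hours rule already in 9.9 and the unit of 14.5. Express its censoring times in hours on the same scale, and delete the sentence that justifies day-level censoring by the day unit. Copying 14.5 would not achieve this, because 14.5 also censors at the day of an assessment.

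In the same edit, state that the last-microscopy rule applies to participants who do not clear, who discontinue for lack of efficacy or who die of malaria. If that is not the intention, reconcile it with the Section 7 rule of censoring at medication intake.

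The cost is SAP wording and code. Dose date and time are recorded (Protocol 6.4). Film clock times are not promised in so many words, but the ±30-minute window in SAP 9.4 implies them. The 6-hour confirmation of a zero count is weaker evidence, because it could be applied from nominal timepoints.

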15.1 Adverse Events

Adverse Events will be coded according to the latest MedDRA version available at the time of database lock and assigned to a SOC and a PT. The severity of AEs will be graded using CTCAE v5.0.

Treatment-emergent AEs (TEAEs) are those events with onset dates on or after the first administration of study intervention.

Any AE occurring before the administration of study intervention on Day 1 and resolved before administration of study intervention or not worsening after administration of study intervention will be included in the AE listings but will not be included in the summary tables (unless otherwise stated). These will be referred to as “pre-treatment” AEs.

Related AEs are those AEs with relationship to study treatment reported by the investigator as related or those of unknown relationship.

Serious AEs are those events reported on the AE eCRF form with the serious field ticked “Yes” or with unknown seriousness.

AEs leading to study discontinuation are those AEs that were referenced as reason for early study termination on the eCRF study termination page.

AEs of special interest (AESIs) are liver (Aminotransferase (AT) increase, Total Bilirubin (TB) increase) and central nervous system (CNS) signals which will be specifically followed-up through laboratory surveillance and a specific physical examination at specific visits during the study. AESIs are AEs which have been ticked to qualify as events of special interest per protocol on the AE eCRF form.

Group/SOC terms and PTs within each group/SOC will be sorted alphabetically.

If a participant experiences more than one occurrence of the same TEAE during the trial, the participant will only be counted once for that treatment (the worst severity and the worst relationship to trial treatment will be tabulated).

In case a participant had events with missing and non-missing grades, the maximum of the non-missing grades will be displayed. AEs with missing classification concerning study intervention relationship will be considered related to the study intervention.

Incomplete AE-related dates will be handled as described in Section 9.13.

AE listings will include all AEs (whether treatment-emergent or not).

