#### **9.4.2 Safety Analyses**

The primary endpoint of Part A and a secondary endpoint of Part B is defined as incidence, severity, and seriousness of study intervention-related TEAEs, as per CTCAE v5.0.

Generally, AEs will be analyzed with frequency tables displaying number of participants with  $\geq 1$  AE by SOC and PT coded with MedDRA dictionary current at the time of database lock. Additionally, for the analysis of any safety endpoint the following definitions apply:

- TEAEs are defined as AEs which started at or after the administration of study intervention (study treatment) or which started prior to the first administration of study intervention but worsened after the dose intake, until the last scheduled assessment will be regarded as treatment-emergent, but before established rescue antimalarial treatment is administered, if required. All AEs will be documented, and will include the Investigator term, the preferred term, start and end date of AE, duration (days), severity, study intervention relationship, action taken and outcome.
- Liver signals (AT increase, TB increase) and CNS signals will be considered AESIs and specifically followed-up through laboratory surveillance and a specific physical examination at specific visits during the follow-up.
- Abnormal laboratory findings and other abnormal investigational findings should not be reported as SAEs unless they are associated with clinical signs and symptoms, lead to treatment discontinuation, or are considered otherwise medically important by the Investigator.

Examples of medically important findings include:

- Requirement for treatment or any other therapeutic intervention.
- Necessity for further diagnostic evaluation (excluding repetition of the same procedure to confirm the abnormality).
- Association with clinical signs or symptoms that may have a significant clinical impact, as determined by the Investigator.
- Clinically significant changes (as assessed by the Investigator) of any laboratory parameter throughout the study (compared to the last assessment prior to any study intervention).

Note: if the abnormal results were already present at Baseline with the same severity, it will be recorded as medical history.

Safety endpoints will primarily be analyzed on the SAF.

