2.0	21OCT2024	PPD	Updates in Section 7 and 14.5 to include only participants who had a temperature $>37.5^{\circ}\text{C}$ at the pre-dose visit or during the 24 hours following dosing will be included. If the fever medication was taken prior to dosing, participants will still be included for analysis. Strategies for intercurrent events will not apply.

4 Purpose of the Integrated Analysis Plan

The purpose of this Integrated Analysis Plan (IAP) is to document technical and detailed specifications for the primary, secondary and **CCI** analyses of data collected for protocol MS201618_0033. Results of the analyses described in this IAP will be included in the Clinical Study Report (CSR). Additionally, the planned analyses identified in this IAP may be included in regulatory submissions or future manuscripts. Any post-hoc, or unplanned analyses performed to provide results for inclusion in the CSR but not identified in this prospective IAP will be clearly identified in the CSR.

The IAP is based on the study protocol and protocol amendments and is prepared in compliance with ICH E9. It describes analyses planned in the protocol version 3.0 with changes documented in section 7 below. The IAP may be updated as a result of protocol amendments, clarifications, or corrections. The IAP will not be updated with every protocol amendment unless protocol changes affect data analyses described in this IAP. Any updates to the IAP prior to data review will be documented in the modification history above and will be reviewed and approved accordingly. Any changes to the described analysis occurring after data review will be labeled as such and documented in the CSR.

The wording used in this IAP is chosen to best match the respective wording in the study protocol template, the CSR template, CDISC requirements and special requirements for table layouts. Therefore, the following approach is used:

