9.12 Definition of On-treatment Period

The on-treatment period is defined as the time from the date of first dose of study intervention to the date of premature study termination, end of study visit date or database lock date or death, whichever occurs first.

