9.13 Imputation of Missing Data

No action will be taken to handle missing data. A participant who withdraws prior to the last planned observation in a study period will be included in the analyses up to the time of discontinuation.

Unless otherwise specified, all data will be evaluated as observed, and no imputation method for missing values will be used.

To determine treatment-emergent AEs, incomplete AE-related start dates will be imputed as follows:

- In case the onset date is missing completely or missing partially but the onset month and year, or the onset year, are equal to the start of study intervention then the onset date will be imputed by the minimum of start of study intervention and AE resolution date (if not missing). If AE resolution date is completely or partially missing, then the study intervention date will be used.
- In all other cases, the missing onset day or missing onset month will be imputed by 1.

Incomplete or missing AE stop dates will not be imputed, since no durations of AEs are planned to be derived.

Missing or partially missing dates for Medical History will not be imputed.

In order to allocate medications to either previous or concomitant, the following imputation rules for (partially) missing start dates will be applied:

- If the day is missing, it will be imputed by the 1st day of the month.
- If both day and month are missing the date will be imputed by 1st January.
- If the date is completely missing, no imputation will be performed.

10 Study Participants

The subsections in this section include specifications for reporting participant disposition and study intervention/study discontinuations. Additionally, procedures for reporting protocol deviations are provided.

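### SAP 15.1 counts treatment-emergent adverse events on a different, undeclared rule from protocol 9.4.2: no stop at rescue treatment, and no clear place for pre-dose events that worsen

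*SAP*

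**What the plan says.** Protocol 9.4.2 names the endpoint: "The primary endpoint of Part A and a secondary endpoint of Part B is defined as incidence, severity, and seriousness of study intervention-related TEAEs". Its TEAE definition covers events that start at or after dosing and also those "which started prior to the first administration of study intervention but worsened after the dose intake". The window runs to the last scheduled assessment, "but before established rescue antimalarial treatment is administered, if required".

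SAP 15.1 defines the term in one sentence: "Treatment-emergent AEs (TEAEs) are those events with onset dates on or after the first administration of study intervention". The next paragraph deals with events that began before dosing. Those that "resolved before administration of study intervention or not worsening after administration of study intervention will be included in the AE listings" are labelled pre-treatment and kept out of the summary tables. SAP 15.1 gives no end to the TEAE window. SAP 9.12 defines a general period: "The on-treatment period is defined as the time from the date of first dose of study intervention to the date of premature study termination", with the end-of-study visit, database lock and death as the other possible ends. Rescue treatment is not among them.

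On departures from the protocol, SAP Section 4 says: "It describes analyses planned in the protocol version 3.0 with changes documented in section 7 below". Section 7 contains no entry on the TEAE definition.

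**The concern.** Related TEAEs are the primary endpoint of Part A, so the rule for what counts as treatment-emergent is the rule for the endpoint. The SAP differs from the protocol in two places without saying so.

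The first is the end of the window. A participant who fails early and is rescued receives another antimalarial while still being followed. The protocol keeps events that start after that point out of the TEAE count, and the SAP lets them in.

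The second is the event that is present before dosing and gets worse afterwards. This is a realistic case here. Adverse events are collected from consent, in acutely ill patients. Nausea, vomiting and abdominal discomfort are scored as malaria symptoms (protocol Appendix 6), while nausea, vomiting and abdominal pain are named as effects of both compounds (protocol 2.3.1).

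Cohorts B1 to B3 were not enrolled, so Part A and Cohort B0 supply all the safety evidence, with small denominators and no comparator. A count that depends on which document the programmer followed would be hard to interpret.

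**Working it through.** The documents give no figure that depends on the TEAE definition, so there is nothing to reproduce. The check is a comparison of text, followed by a rough sizing.

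**Step 1: the rules side by side**

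| Type of event | Protocol 9.4.2 | SAP 15.1 and 9.12 |
|---|---|---|
| Starts at or after dosing, no rescue given | TEAE | TEAE |
| Starts before dosing, worsens after it | TEAE | Fails the TEAE sentence, but is not pre-treatment either |
| Starts before dosing, resolves first or does not worsen | Not a TEAE | Pre-treatment, listing only |
| Starts after rescue antimalarial | Not a TEAE | TEAE |
| Change declared in SAP Section 7 | n/a | No |

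**Step 2: follow each discordant row into the outputs**

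- *Worsened pre-dose event.* The pre-treatment paragraph implies it should be summarised. However, the summaries in SAP 15.1.1 are built on TEAEs, and the only definition of a TEAE requires onset at or after dosing. A programmer who codes that sentence drops the event. The possible effect is to lower the count.
- *Post-rescue event.* It enters the all-TEAE and serious-TEAE tables directly, and the AESI table if it is of that type. It enters the related-TEAE endpoint if the investigator calls it related. SAP 15.1 also treats a missing or unknown relationship as related. The possible effect is to raise the count.

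**Step 3: size per participant**

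The inputs are 12 participants planned in Part A and 25 in Cohort B0. If a participant's only qualifying event is reclassified, incidence moves by:

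- Part A: 1/12 = 8.3 percentage points
- Cohort B0: 1/25 = 4 percentage points

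A participant with another qualifying event does not move the incidence at all.

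**Step 4: how many Part A participants could have post-rescue follow-up**

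The assumption is that each predicted failure is rescued. The expected number is n × p, and P(at least one) = 1 − (1 − p)^n, with n = 12.

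| Source of p | p | Expected number | P(at least one) |
|---|---|---|---|
| Early treatment failure, protocol 2.3.1, low | 0.025 | 0.3 | 26% |
| Early treatment failure, protocol 2.3.1, high | 0.40 | 4.8 | 99.8% |
| 1 − predicted Day 28 response, protocol 4.3, low (1 − 0.922) | 0.078 | 0.9 | 62% |
| 1 − predicted Day 28 response, protocol 4.3, high (1 − 0.591) | 0.409 | 4.9 | 99.8% |

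These are participants in whom the rescue rule could matter. They are not counts of reclassified events, which the documents give no means to estimate.

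**The case against.** The strongest reply is that the SAP does not abandon worsening. A reader might infer from the definition sentence that classification is by onset date alone and that the worsening condition has been dropped. The next paragraph does not support that: it keeps out of the summaries only pre-dose events that resolved or did not worsen, which makes sense only if worsened ones are meant to be summarised. Nor does SAP 9.13 settle it. Its text, "To determine treatment-emergent AEs, incomplete AE-related start dates will be imputed as follows", is an imputation rule that any TEAE definition would need, the protocol's included. This objection stands. The defect is two adjoining paragraphs that do not fit together.

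A second reply concerns rescue. A reader might infer that the SAP attributes the rescue drug's effects to M5717-pyronaridine. In general it does not. The endpoint counts related events, and protocol Appendix 4 tells investigators to weigh concomitant therapy when judging causality. Nor is a post-rescue event necessarily due to rescue: the protocol works with a terminal half-life of 155 hours. This limits the effect on the related-TEAE endpoint. It does not remove it, because missing or unknown relationships default to related, and the all-TEAE tables have no such filter.

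Third, the capture rules narrow the opening for pre-dose events. Screening is at most 12 hours before dosing, findings within expectation for the disease are not adverse events, and severe malaria is recorded separately. How a worsened symptom would be entered on the case report form cannot be seen. It might be given a new, post-dose onset, in which case the SAP sentence would catch it.

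Finally, all adverse events and medications are listed and rescue dates are recorded. With 37 planned participants (12 + 25), either count could be rebuilt by hand. That is true, but a reader of the summary tables would not know a rebuild was needed.

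**Conclusion.** The point holds: SAP 15.1 is wrong as written. The absence of the protocol's stop at rescue is plain, has no counter-text in the SAP and is not declared in Section 7. The worsening part is an internal mismatch, which costs events only if the definition sentence is programmed literally.

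The documents do not support a claim that toxicity is understated overall. One difference can raise the count and the other can lower it, so the net error is unknown in size and sign. The shifts of 8.3 and 4 points are conditional on the reclassified event being the participant's only qualifying one. The range of 0.3 to 4.8 participants rests on pre-trial model predictions and on every early failure being rescued.

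A reader might also infer that a participant rescued on Day 4 contributes 39 of 42 follow-up days (42 − 3) after rescue. That is an upper bound, because protocol 6.8.1 allows rescue to accompany withdrawal from the study, although protocol 7.1 keeps participants in follow-up. For Part A participants who do not fail, the Schedule of Activities places rescue at Day 43, so little time is affected.

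**What to change.** - Extend the TEAE sentence in SAP 15.1 to include onset before first dose with worsening after dosing. The sentence and the pre-treatment paragraph then cover every event between them.
- Apply the protocol's stop at rescue to the main TEAE tables. If the sponsor prefers to count through rescue, declare the removal in Section 7 with a reason. Without the stop, the SAP rule should not be described as the protocol's definition.
- In either case, flag events that start after rescue antimalarial treatment and tabulate them separately by part, so that none is lost.

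The cost is one SAP paragraph, one derived flag and one extra table. The flag needs no new data: rescue start dates go on the concomitant medication page (protocol 6.8.1), and SAP 14.1 already sets out how rescue medication is identified. The change is to analysis only.
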